### **Ethics**

Study conducted in accordance with the Declaration of Helsinki and approved by institutional ethics committee. Written informed consent obtained from all participants.

### **STATISTICAL ANALYSIS PLAN**

#### **1. Data Handling**

Data analyzed using SPSS / R

Missing data handled using listwise deletion

#### **2. Normality Testing**

Shapiro–Wilk test applied to all variables

#### **3. Between-Group Analysis**

Independent samples t-test

Mann–Whitney U test (if non-normal)

#### **4. Within-Group Analysis**

Paired t-test

Wilcoxon signed-rank test

#### **5. Effect Size**

Cohen's d for parametric tests

r for non-parametric tests

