### **Outcomes**

**Primary Outcomes:** Peripheral immune cell counts (leukocytes, lymphocytes, neutrophils, monocytes) Inflammatory cytokines (IL-6, TNF- $\alpha$ , CRP)

**Secondary Outcomes:** Immunoglobulins (IgA, IgG, IgM) Cortisol levels  $VO_{2max}$

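### Effect sizes are planned only as unit-free d or r, switched variable by variable by a normality test, with no between-group difference in original units and no confidence interval, at 10 per group

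*Protocol*

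**What the plan says.** The Protocol contains a part headed as the statistical analysis plan. Its section 5 (Effect Size) consists of two lines: "Cohen's d for parametric tests" and "r for non-parametric tests". It gives no formula for either measure, no small-sample correction and no interval.

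Which measure applies depends on earlier sections. Section 2 has the "Shapiro–Wilk test applied to all variables". Section 3 then lists the "Independent samples t-test" with the Mann-Whitney U test as the alternative for non-normal data. Section 4 adds paired t and Wilcoxon tests within each group, and section 6 sets a two-tailed 0.05 threshold.

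The Outcomes section makes seven variables primary: "Peripheral immune cell counts (leukocytes, lymphocytes, neutrophils, monocytes"), plus IL-6, TNF-α and CRP. Participants gives 10 per group. Data Collection gives a baseline and an 8-week value. No estimate in original units and no confidence interval is mentioned anywhere in the document.

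**The concern.** There are two problems, and one minor addition.

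**The metric follows the pretest.** If one cytokine passes Shapiro-Wilk and another fails, the first is reported as d and the second as r. The two numbers cannot be read side by side, yet the Objective is to compare two programmes across a panel of markers.

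**The size of effect is stated without its uncertainty.** A unit-free point estimate beside a p-value does not tell the reader how large a difference the data still allow. In a trial of 20 people that is the main thing a reader needs to know about a non-significant result. Cell counts and CRP also have units that readers understand, and a difference in those units is not planned.

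**Small-sample bias.** Uncorrected d overstates the true standardised difference a little at this size.

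**Working it through.** **No figure to reproduce.** The document states 10 per group but gives no assumed effect, SD or power. The checks below take from it n = 10 per group, a two-sided 0.05 level, an independent t-test (18 df with complete data) and a paired t-test (9 df). The assumptions are normal data, complete data, r = Z/√N for the rank test, paired d standardised by the SD of the differences, and |d| = 0.8 as a large effect.

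**1. d and r are on different scales.** For normal data with true standardised difference d, the probability that a member of one group exceeds a member of the other is p = Φ(d/√2). The large-sample value of r is √3 × (p − 0.5).
- d = 0.5: p = 0.638, r = 1.732 × 0.138 = 0.24
- d = 0.8: p = 0.714, r = 1.732 × 0.214 = 0.37

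At 10 against 10, r cannot exceed 50/√175/√20 = 0.845, whereas d has no upper limit.

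**2. How easily the metrics mix.** Suppose all seven primaries were exactly normal and independent, with Shapiro-Wilk at 5%. The chance that at least one switches is 1 − 0.95^7 = 30% with one test per variable, or 1 − 0.95^14 = 51% with one test per group. Correlation between outcomes would lower these figures and real non-normality would raise them.

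**3. Precision of the unadjusted difference.** The 95% half-width in SD units is t(0.975, 18) × √(2/10) = 2.101 × 0.447 = 0.94. An observed |d| must therefore exceed 0.94 for p < 0.05.

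Noncentral-t 95% intervals for d at 10 per group:

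| Observed d | 95% CI |
|---|---|
| 0 | −0.88 to 0.88 |
| 0.5 | −0.40 to 1.38 |
| 0.8 | −0.12 to 1.70 |
| 0.9 (p = 0.059) | −0.04 to 1.81 |

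Even the interval at d = 0 reaches past 0.8. The upper limit rises with observed d, so with complete data every non-significant t-test leaves a large effect open in at least one direction. Power is 19% at a true d of 0.5 and 40% at 0.8, so such results are likely.

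**4. Bias of d.** The exact correction factor is J(df) = Γ(df/2) / [√(df/2) × Γ((df−1)/2)].
- Between groups: J(18) = 0.958, so d is inflated by 1/0.958 − 1 = 4.4%.
- Paired: J(9) = 0.914, so d is inflated by 9.4%.

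The between-group bias is 0.02 to 0.03 at d of 0.5 to 0.8, against a sampling SD of d of about 0.47 to 0.50. In 200,000 simulated trials the signed r averaged 0.234 against a large-sample 0.239, and 0.362 against 0.371. That is about 2% low, not high.

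**5. What baseline adjustment would gain.** With the baseline value as covariate (17 df) and baseline to follow-up correlation ρ, the expected half-width is about t(0.975, 17) × √[(2/10)(1 + 1/16)(1 − ρ²)]. The factor 1 + 1/16 allows for chance baseline imbalance.
- ρ = 0.5: 2.110 × √(0.2125 × 0.75) = 0.84 SD
- ρ = 0.7: 2.110 × √(0.2125 × 0.51) = 0.69 SD

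The document gives no correlation; 0.5 to 0.7 is an assumed range.

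**The case against.** The strongest reply is that this is mostly silence. Section 5 adds effect sizes to p-values, which is better than p-values alone, and it excludes neither intervals nor raw differences. That is true of the interval taken by itself. It does not cover the whole point: section 5 does choose its measures, and with sections 2 and 3 it ties them to a pretest.

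Several stronger readings are tempting and should not be drawn.

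- *The planned effect sizes are biased upward.* This is so only for uncorrected d, by an amount that is trivial beside its sampling error. It is not so for signed r.
- *Effects cannot be compared across outcomes.* Between-group d values computed the same way share one scale. The difficulty arises when one outcome gets d and another r, or when between-group d is set beside paired d.
- *Most non-significant results will allow large differences either way.* Both −0.8 and +0.8 lie inside the interval only when observed |d| is below about 0.08, roughly 14% of non-significant results if the true difference is zero. The claim that holds is a large difference in at least one direction.
- *The trial will report p > 0.05 as equivalence.* No section says so. The Objective is to compare, and section 6 only sets the level. Misreading is a risk, not a plan.

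It is also fair to say that the root cause is the sample size, and that removing r and within-group d while leaving the rank and paired tests in place would create a mismatch. The fix allows for both.

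**Conclusion.** The point stands in a limited form and is worth correcting. As written, the plan can put primary outcomes on two scales within one table (d of 0.5 beside r of about 0.24 for the same true effect, given r = Z/√N). It plans neither a difference in original units nor an interval, where the unadjusted 95% half-width is 0.94 SD. A non-significant result will usually remain compatible with a large difference in at least one direction.

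The 4.4% inflation of between-group d is a minor secondary matter. The precision figures assume normal, complete data. The plan has "Missing data handled using listwise deletion", so any loss would widen the intervals, and 9 or 8 per group would raise the inflation to 5.0% or 5.8%.

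**What to change.** Change sections 3 and 5 together.

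1. For every outcome, estimate the between-group difference at 8 weeks adjusted for the baseline value already collected. Give it in original units, or as a ratio of geometric means for markers analysed on the log scale, with a 95% CI. Make this the basis of the between-group conclusion.
2. Report Hedges' g with a 95% CI as the single standardised between-group measure for all outcomes.
3. Keep any rank tests as sensitivity analyses, so that their p-values do not compete with the interval.
4. Label the within-group results descriptive.

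A sentence saying that p above 0.05 is not evidence of equivalence would be a useful safeguard. The statistical methods in the Protocol's main Statistical Analysis section should be brought into line.

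The cost is slightly more analysis work, one degree of freedom for the covariate, and standardised effects about 4% smaller than Cohen's d. No new data are needed. If the baseline to follow-up correlation is 0.5 to 0.7, the half-width falls from 0.94 to about 0.84 to 0.69 SD. The interval will show how imprecise 10 per group is; it will not remove that imprecision.

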#### **6. Significance Level**

$p < 0.05$  (two-tailed)

#### **7. Software**

IBM SPSS Statistics / R Statistical Software
